## 2. Response Criteria for CLL

Radiographic and clinical assessments in accordance with the criteria established by IWCLL [2] will be used to determine response. CT scan is the preferred method for evaluating tumor response. The spleen and liver should also be assessed by physical examination.

- Selection of target (measured) lesions for imaging or physical examination:
  - Up to six of the largest nodes, nodal masses, and extranodal lesions selected to be clearly measurable in 2 diameters at baseline.
  - A measurable node must have a longest transverse diameter of a lesion (LDi) > 1.5 cm. A measurable extranodal lesion (e.g., hepatic nodules) should have an LDi > 1.0 cm.
  - Nodes should preferably be from disparate regions of the body and should include, where applicable, mediastinal and retroperitoneal areas.
  - Non-nodal lesions include those in solid organs (e.g., liver, spleen, kidneys, and lungs), gastrointestinal (GI) involvement, cutaneous lesions, or those noted on palpation.
  - If possible, they should be from disparate regions of the body.
  - If possible, they should include mediastinal and retroperitoneal areas of disease whenever these sites are involved.
- Selection of non-target (non-measured) lesions for imaging or physical examination:
  - Any lesions not selected as target (measured) and truly assessable lesions should be considered not measured.
  - These lesions include any nodes, nodal masses, and extranodal lesions not selected as target (measured) or that do not meet the requirements for measurability but are still considered abnormal, as well as truly assessable lesions, which are any sites of suspected disease that would be difficult to follow quantitatively with measurement, (e.g., cutaneous, GI, bone, spleen, liver, kidneys, pleural or pericardial effusions, ascites, leptomeningeal lesions/disease) and other lesions that cannot be confirmed and followed by imaging.

## 3. Complete Response (CR)

*To satisfy the criteria for CR, all of the following criteria must be met and must persist for ≥ 8 weeks:*

- No evidence of new disease
- ALC in peripheral blood of <  $4 \times 10^9/L$
- Regression of all target nodal masses to normal size (i.e.,  $\leq 1.5$  cm in the longest diameter for nodes that were considered large at baseline and  $\leq 1.0$  cm in the longest perpendicular diameter for nodes that were considered small at baseline)

- Normal spleen and liver size
- Regression to normal of all nodal non-target disease and disappearance of all detectable non-nodal, non-target disease
- No disease-related constitutional symptoms
- Peripheral blood counts meeting all of the following criteria:
  - ANC  $\geq 1.5 \times 10^9/L$  without need for exogenous growth factors (e.g., G-CSF)
  - Platelet count  $\geq 100 \times 10^9/L$  without need for exogenous growth factors
  - Hemoglobin  $\geq 110$  g/L (11.0 g/dL) without red blood cell transfusions or need for exogenous growth factors (e.g., erythropoietin)

Notes:

- *Morphologically negative bone marrow* is defined as  $< 30\%$  of nucleated cells and no lymphoid nodules in a bone marrow sample that is normocellular for age.
- Patients who fulfill all the criteria for a CR (including bone marrow criteria) but who have a persistent anemia, thrombocytopenia, or neutropenia that is related to prior or ongoing drug toxicity (and not to CLL) will be considered as a CR with incomplete marrow recovery (CRi).

#### 4. Partial Response (PR)

To satisfy criteria for PR, all of the following criteria must be met and must persist for  $\geq 8$  weeks:

- No evidence of new disease
- Decrease in peripheral blood ALC by  $\geq 50\%$  from baseline
- A decrease by  $\geq 50\%$  from the baseline in the SPD (sum of the products) of the target nodal lesions
- In patients with enlargement of the spleen or liver at baseline:
  - Normal spleen size, or a decrease by  $\geq 50\%$  from baseline in the pretreatment enlargement of the vertical dimension below the left costal margin (by palpation) or in total vertical dimension (by imaging)
  - Normal liver size, or a decrease by  $\geq 50\%$  from baseline in the pretreatment enlargement of the liver total vertical dimension at the right costal margin (by percussion) or a qualitative decrease in liver size (by imaging)
- No increase in the size of the liver or spleen
- No increase in the size of non-target disease
- No persistent (lasting  $> 4$  weeks) worsening of disease-related constitutional symptoms
- Peripheral blood counts meeting any of the following criteria:

- ANC  $\geq 1.5 \times 10^9/L$  or  $\geq 50\%$  increase over baseline without need for exogenous growth factors (e.g., G-CSF)
- Platelet count  $\geq 100 \times 10^9/L$  or  $\geq 50\%$  increase over baseline without need for exogenous growth factors
- Hemoglobin  $\geq 110$  g/L (11.0 g/dL) or  $\geq 50\%$  increase over baseline without red blood cell transfusions or need for exogenous growth factors (e.g., erythropoietin)

**Note:** Patients who achieve a PR by IWCLL 2008 criteria [2] in all parameters except lymphocyte count will be considered PR with lymphocytosis. Patients with a PR with lymphocytosis will not be considered to have achieved a PR until there is a 50% reduction in ALC from baseline was achieved or ALC  $< 4 \times 10^9/L$ .

**Note:** Marrow should have at least a 50% reduction in marrow infiltrate or B-lymphoid nodules

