### **1.6.5. Chronic Lymphocytic Leukemia (CLL)/Small Lymphocytic Lymphoma (SLL)**

CLL is the most prevalent leukemia in the western world. SLL is essentially a more nodal form of the disease without peripheral blood involvement [19, 55]. In 2015, there were an estimated 14,620 cases and 4,650 deaths from CLL/SLL.

CLL/SLL is grouped with the indolent lymphomas and is incurable; however, typically it is treatable. Depending on the stage, genetic/other prognostic factors and symptoms at diagnosis, patients may be observed initially and only treated when symptoms such as adenopathy or cytopenias develop [19, 55, 60].

There are a multitude of regimens available for therapy and the choice of 1 regimen or agent over another depends on the patient's prognostic factors, performance status, and symptoms. For more elderly patients with comorbidities, chlorambucil (alone or in combination with obinituzumab or ofatumumab, both anti-CD20 antibodies) can be used. The combinations have shown superior outcomes vs. single-agent chlorambucil [19, 60, 61]. Alternatively, bendamustine with rituximab can also be used. For more fit patients, fludarabine may be used in combination with rituximab and cyclophosphamide (for both upfront and relapsed/refractory patients) [19, 60, 61].

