**Table 6: By-Cohort Inclusion Criteria for Phase 2a Cohorts**

Cohort Number (short descriptor)	Inclusion Criteria
1 (FL)	Patients with FL Grade 1 to 3A who have received $\geq 1$ prior treatment regimen.
2 (Combination Cohort)	Patients with FL Grade 1 to 3A who have received $\geq 1$ prior treatment regimen. In addition to receiving cerdulatinib, this cohort will also receive rituximab IV at 375 mg/m  during Cycle 1 on Days 1, 8, 15, and 22 and during Cycles 4, 6, 8, and 10 on Day 1 only.
3 (aNHL)	
Patients with aggressive NHL (aNHL), defined as DLBCL, FL 3B, MCL, and transformed NHL. These patients have relapsed from <math>\geq 1</math> but <math>\leq 3</math> prior cytotoxic chemotherapy regimens with an anti CD20 antibody, (e.g., R-CHOP, BR). Patients must have received an anthracycline based therapy unless anthracyclines were deemed inappropriate in the judgement of the investigator.
 
Patients must have either relapsed following ASCT or not be candidates (ineligible) for ASCT, defined as meeting any of the following criteria [1]: a) age <math>\geq 70</math> years; b) DLCO <math>< 50\%</math> by pulmonary function tests; c) FEV1/FVC <math>< 60\%</math> predicted by pulmonary function tests; d) LVEF <math>< 45\%</math> by MUGA or echocardiogram; e) uncontrolled arrhythmia; f) calculated creatinine clearance (Cockcroft-Gault) <math>\leq 60</math> mL/min; g) other comorbidities (e.g., medical conditions or psychosocial conditions) that would likely result in an unacceptably high probability of treatment/transplant related morbidity and mortality in the judgement of the investigator (e.g., high HCT-CI, CIRS, scores); h) refusal of ASCT.
 
(Note: Antibody drug conjugates (ADC) count as cytotoxic chemotherapy. Salvage chemotherapy prior to ASCT with or without maintenance therapy counts as one regimen.)

4 (CLL/SLL)	Patients with CLL/SLL who have received $\geq 1$ prior treatment regimen.
5 (PTCL NHL)	Patients with PTCL NHL who have received $\geq 1$ prior systemic treatment regimen for PTCL. In patients with CD30-expressing PTCL, prior treatment must include a CD30-directed antibody (e.g., brentuximab vedotin).
6 (CTCL NHL)	Patients with CTCL NHL who have received $\geq 1$ prior systemic treatment regimen for CTCL.

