### **11.2.2. Phase 2a Sample Size**

Each of the 6 cohorts will consist of approximately 20 to 50 patients with relapsed or refractory disease. Initial enrollment into any cohort will be up to 20 patients; cohorts may be expanded to 40 to 50 evaluable patients. A total of approximately 240 patients are planned. If fewer than 2 responses are seen in the first 20 patients, enrollment in the cohort will be closed, as the upper bound (UB) of the 95% confidence interval would be approximately 25%. If 2 or more responses are seen, the cohort may be expanded.

Patients in Cohorts 1, 3, 4, 5, and 6 will receive single-agent cerdulatinib. Patients in the Cohort 2 will receive cerdulatinib in combination with rituximab. The composition of each cohort is described in [Table 6](#).

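### Appendix 4 gives two conflicting lymphocyte conditions for a CLL partial response, which can change individual Cohort 4 responses and the cohort's closing decision

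*Protocol*

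**What the plan says.** **PR list.** Protocol Appendix 4, item 4, opens its list for a CLL partial response by saying that "all of the following criteria must be met and must persist for" at least 8 weeks. One item is "Decrease in peripheral blood ALC by" at least 50% from baseline. The item gives no absolute-count alternative and no exemption for a low baseline.

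**PR note.** The first note under the list concerns patients who reach PR by the IWCLL 2008 criteria "in all parameters except lymphocyte count will be considered PR with lymphocytosis". It says they "will not be considered to have achieved a PR until there is a 50% reduction in ALC from baseline was achieved or ALC" is below 4 × 10^9/L.

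**CR list.** Item 3 of the same appendix asks for "ALC in peripheral blood of" less than 4 × 10^9/L and sets no percentage fall.

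**Who is scored.** Cohort 4 in Table 6 is "Patients with CLL/SLL who have received" at least one prior regimen, with no baseline ALC in that criterion. Section 1.6.5 says "SLL is essentially a more nodal form of the disease without peripheral blood involvement". Section 8.1 assigns the Lugano criteria to NHL and the IWCLL criteria to CLL, and does not name SLL.

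**What depends on it.** Section 11.2.2 says: "If fewer than 2 responses are seen in the first 20 patients, enrollment in the cohort will be closed". SAP 5.2 repeats the rule. SAP 7.8 and SAP 8 restrict aggregate efficacy to FL patients in Cohorts 1 and 2 and PTCL patients in Cohort 5. Cohort 4 efficacy is listed only.

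**The concern.** The list and its note give different answers for the same patient. Someone whose nodes and other parameters meet PR, and whose ALC is below 4 × 10^9/L without having halved, is not a partial responder by the list but can be one by the note. The order of the categories is also disturbed. This patient satisfies the lymphocyte item for the better response (CR) and fails it for the lesser one (PR) unless an already low count is cut in half.

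At stake are the responses recorded for individual Cohort 4 patients and the decision to close or expand the cohort. That decision turns on a single response: 1 of 20 closes the cohort and 2 of 20 allows expansion.

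**Working it through.** **1. Where the two conditions part.** Let b be baseline ALC and x on-treatment ALC, both in 10^9/L.

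- List: x ≤ b/2.
- Note: x ≤ b/2, or x < 4.
- They differ only when b/2 < x < 4. This requires b/2 < 4, so b < 8.

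| Baseline → on treatment | Fall | PR list item | PR note | CR list item (x < 4) |
|---|---|---|---|---|
| 6 → 3.5 | 2.5/6 = 41.7% | not met | met | met |
| 1.5 → 1.5 | 0% | not met | met, if the note is taken to apply | met |
| 1.5 → 0.75 | 50% | met | met | met |
| 2.0 → 0.9 | 1.1/2.0 = 55% | met | met | met |

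The first two rows are the conflict. The last two show that a low baseline alone does not create it.

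**2. The plan's own figure.** Section 11.2.2 justifies the closing rule by an upper 95% bound of about 25%. The exact two-sided (Clopper-Pearson) upper limit for x responses in n is the 0.975 quantile of Beta(x + 1, n − x).

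- 1/20: interval 0.13% to 24.87%, which reproduces the stated 25%.
- 0/20: upper limit 16.84%.
- 2/20: interval 1.23% to 31.7%, and the cohort may be expanded.

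**3. Effect on the closing decision.** The documents give no share of patients with x < 4 and no halving, so the share is assumed. Suppose m of the first 20 are affected and, as the extreme case, have no chance of being counted as responders under the list. With N = 20 − m and true rate p,

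P(close) = (1 − p)^N + N p (1 − p)^(N − 1).

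For p = 0.20 and m = 0: 0.8^20 + 20 × 0.2 × 0.8^19 = 0.0115 + 0.0576 = 0.069. For m = 8: 0.8^12 + 12 × 0.2 × 0.8^11 = 0.0687 + 0.2062 = 0.275.

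| True rate | m = 0 | m = 2 | m = 4 | m = 8 |
|---|---|---|---|---|
| 20% | 6.9% | 9.9% | 14.1% | 27.5% |
| 15% | 17.6% | 22.4% | 28.4% | 44.3% |

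**4. Why these are upper bounds for each m.** An affected patient can still be a CR, or can halve the count and be a PR. Suppose, as a further assumption, that 5 points of the 20% rate are CRs. Then m patients respond with probability 0.05 and the rest with 0.20. For m = 8:

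- P(0) = 0.0687 × 0.95^8 = 0.0687 × 0.6634 = 0.0456.
- P(1) = 0.2062 × 0.6634 + 0.0687 × 8 × 0.05 × 0.95^7 = 0.1368 + 0.0192 = 0.1560.
- P(close) = 20.2%, against 27.5% without that credit.

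For m = 2 the same calculation gives 9.1%, against 9.9%.

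**5. Cross-check on a different footing.** Let s be the assumed share of responders under the note who qualify only through ALC < 4. The list then sees a rate of p(1 − s). At p = 20% the closing probability goes from 6.9% to 10.2% (s = 10%), 17.6% (s = 25%) or 39.2% (s = 50%). The two readings give opposite decisions on the same 20 patients with probability 3.3%, 10.6% or 32.3%. At p = 30% those probabilities of opposite decisions are 0.8%, 3.4% and 16.8%. The 50% share goes beyond the 8-of-20 case in step 3.

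**The case against.** The strongest reply is that the note settles the matter. It addresses patients who miss PR on lymphocytes alone and says what they then need, so as the specific rule it qualifies the general list item. An assessor would have to ignore text directly beneath the list to go wrong. This has force for the patient going from 6 to 3.5. It fits less well for a patient who stays at 1.5: the note is framed as PR with lymphocytosis, and this patient never had a raised count. The list meanwhile says that all its items must be met. The conflict is reduced but remains.

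A reader might also infer more than the documents support:

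- **That SLL patients cannot be partial responders.** A halved count meets the list. It is also not settled that the CLL list applies to SLL. Section 1.6.4 counts SLL among the indolent lymphomas, and Lugano has no ALC condition. Against that, the exploratory endpoint speaks of CLL/SLL patients reaching CR, CRi or PR, and CRi is defined only in the CLL criteria. The assignment is a separate gap.
- **That every patient with a baseline below 8 × 10^9/L is affected.** That baseline is necessary but not sufficient. The on-treatment count must also be below 4 × 10^9/L without having halved.
- **That the reported Cohort 4 response rate will be wrong.** Protocol 11.1.3 plans a summary by cohort, but SAP v2.0 expressly changes this and only lists Cohort 4 efficacy.

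**Conclusion.** The inconsistency is real and lies within one item of Appendix 4. It is confined to patients whose on-treatment ALC is below 4 × 10^9/L without having halved. For them it can change the listed Cohort 4 response, and through that the closing decision. No aggregate SAP result for Cohort 4 is affected.

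The size cannot be established from the documents. The rise in closing probability at a true 20% rate, from 6.9% to 9.9%, 14.1% or 27.5%, rests on assumed shares of 2, 4 or 8 of 20. It also gives those patients no credit for a CR or a halved count. Each figure is therefore a ceiling for its assumed share and should not be read as an estimate. The point merits correction because one reclassified patient can reverse a closing decision and the remedy is a wording change.

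**What to change.** In Appendix 4, item 4, reword the PR lymphocyte item to match the note: a decrease of at least 50% from baseline, or ALC below 4 × 10^9/L. A patient whose ALC is below 4 × 10^9/L at baseline and stays there then meets the lymphocyte item and is judged for PR on the other items.

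In Section 8.1, state whether SLL is scored by the CLL (IWCLL) criteria or by Lugano. This is the sponsor's choice, and the item rewording does not make it.

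The cost is one list item and one sentence. No new assessment or data collection is needed.

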## 5. Stable Disease (SD)

To satisfy the criteria for SD, the following criteria must be met:

- No evidence of new disease, i.e., there is neither sufficient evidence of tumor shrinkage to qualify for PR nor sufficient evidence of tumor growth to qualify for definitive disease progression.

## 6. Progressive Disease (PD)

- The occurrence of any of the following events indicates definitive PD:  
Evidence of any new disease that was not present as baseline:
- A new node that measures  $> 1.5$  cm in any diameter
- A new node that measures  $> 1.0$  cm to  $\geq 1.5$  cm in the longest diameter and  $> 1.0$  cm in the longest perpendicular diameter
- New hepatomegaly or splenomegaly
- New non-target disease (e.g., effusions, ascites, or other organ abnormalities related to CLL)

**Note:** Isolated new effusions, ascites, or other organ abnormalities are not sufficient evidence alone of PD unless histologically confirmed. Thus, a declaration of PD should not be made if this is the only manifestation of apparently new disease.

- Evidence of worsening of lymph nodes, spleen or liver, or non-target disease:
  - Increase by  $\geq 50\%$  from the nadir in the SPD of target lesions.

- Increase by  $\geq 50\%$  from the nadir in the product of the perpendicular diameters for any individual node; progression of a single lesion requires that the lesion demonstrates a  $\geq 50\%$  in the product of its diameters and that the lesion now meets the definition of abnormal (a node that was considered large at baseline must now measure  $> 1.5$  cm in the longest diameter and a node that was considered small at baseline must now measure  $> 1.0$  cm in the longest diameter perpendicular to the long diameter of the lesion).
- Increase by  $\geq 50\%$  from the nadir in the longest diameter for any individual node if the node now has a longest perpendicular diameter that is  $> 1.0$  cm.
- In a patient with an abnormal spleen, an increase by  $\geq 50\%$  from the nadir enlargement of the spleen vertical dimension below the left costal margin (by palpation) or in total vertical dimension (by imaging).
- In a patient with an abnormal liver, an increase by  $\geq 50\%$  from the nadir enlargement of the liver total vertical dimension at the right costal margin (by percussion) or a unequivocal qualitative increase in liver size (by imaging).
- Unequivocal increase in the size of non-target disease (e.g., effusions, ascites, or other organ abnormalities related to CLL).
- Transformation to a more aggressive histology (e.g., Richter syndrome) as established histologically.

## 7. Treatment-related Lymphocytosis

Treatment-related lymphocytosis, for the purpose of this protocol, is defined as an elevation in blood lymphocyte count of  $\geq 50\%$  compared to baseline which occurs in the setting of unequivocal improvement in at least 1 other disease-related parameter including lymph node size, spleen size, hematologic parameters or disease symptoms. Patients with isolated lymphocytosis in the setting of reduced disease burden or improvement in hematologic parameters should not be considered to have progressive disease [2].

**8. Response Criteria for Leukemic Forms of Peripheral T-cell Lymphoma (PTCL) (ATLL, PLL, LGL)****A. Response Criteria for ATLL****Table A4-12: Response Criteria for ATLL**

Response	Definition	Lymph Nodes	Extranodal Masses	Spleen, Liver	Skin	Peripheral Blood	Bone Marrow
Complete remission*	Disappearance of all disease	Normal	Normal	Normal	Normal	Normal †	Normal
Uncertified complete remission*	Stable residual mass in bulky lesion	≥75% decrease ‡	≥75% decrease ‡	Normal	Normal	Normal †	Normal
Partial remission*	Regression of disease	≥50% decrease ‡	≥50% decrease ‡	No increase	≥50% decrease	≥50% decrease	Irrelevant
Stable disease*	Failure to attain complete/partial remission and no progressive disease	No change in size	No change in size	No change in size	No change in size	No change	No change
Relapsed disease or progressive disease	New or increased lesions	New or ≥50% increase §	New or ≥50% increase §	New or ≥50% increase	≥50% increase	New or ≥50% increase #	Reappearance

\*Required that each criterion be present for a period of at least 4 weeks.

†Provided that <5% of flower cells remain, complete remission is judged to have been attained if the absolute lymphocyte count, including flower cells, is  $<4 \times 10^9/L$ .

‡Calculated by the sum of the products of the greatest diameters of measurable disease.

§Defined by ≥50% increase from nadir in the sum of the products of measurable disease.

#Defined by ≥50% increase from nadir in the count of flower cells and an absolute lymphocyte count, including flower cells, of  $>4 \times 10^9/L$ .

Source: NCCN 2018 [77].

**B. Response Criteria for PLL**

Investigators are encouraged to use the Workshop on Chronic Lymphocytic Leukemia (IWCLL) Guidelines for the Diagnosis and Treatment of Chronic Lymphocytic Leukemia [2] for CLL (Appendix 4-2).

**C. Response Criteria for LGL**

Response to treatment should be determined by periodic clinical assessments and blood counts (Table A4-13).

**Table A4-13: Response Criteria for LGL**

Complete Response	The complete normalization of blood counts: 
 
hemoglobin >12 g/dL, platelets >150×10^9/L, absolute neutrophil count >1.5×10^9/L, and lymphocytosis <4×10^9/L, and
 
a circulating LGL count of <0.5×10^9/L.
 

Partial Response	An improvement in blood counts: 
 
hemoglobin >8 g/dL, platelets >50×10^9/L, and neutrophils >0.5×10^9/L, and
 
the absence of transfusion requirements.
 

Treatment Failure	Any response not meeting the above criteria within 3 months after the beginning of the treatment.

Source: Bareau, et al [78].

**9. Response Criteria for Cutaneous T-Cell Lymphoma (CTCL)**

All relevant clinical and radiographic information required to make an assessment should be considered. Nodes/lesions should be selected based on criteria described by Olsen, et al [5].

**Table A4-14: Global Response Score**

Global Score a	Definition	Skin	Nodes, Blood, Viscera
CR	Regression of measurable disease	CR	All categories have CR/NI
PR	Regression of measurable disease	CR	All categories do not have a CR/NI and no category has a PD
		PR	No category has a PD and if any category involved at baseline, at least 1 has a CR or PR
SD	Failure to attain CR, PR, or PD representative of all disease	PR	No category has a PD and if any category involved at baseline, no CR or PR in any
		SD	CR/NI, PR, SD in any category and no category has a PD
PD	Progressive disease	PD	PD in any category
Relapse	Recurrence disease in prior CR		Relapse in any category

CR = Complete response; NI = Noninvolved; PR = Partial response; PD = Progressive disease; SD = Stable disease  
Note: It is recommended that not only the proportion of patients who achieve a response or an unfavorable outcome be calculated but a life table account for the length of the interval during which each patient is under observation also be generated.

